#### **5.1.7. Guidelines For Dose Modifications**

For those subjects who continue treatment, the Investigator will evaluate which hematological and/or non-hematological toxicities are attributed to which drug(s), and adjust the dose of one or more of the drugs as recommended below.

If a subject experiences an unacceptable toxicity to cisplatin, the Investigator will be able to withhold drug, reduce dose, or switch to carboplatin. If the Investigator chooses to start treatment with carboplatin, then carboplatin will be administered throughout the study. If a subject also experiences an unacceptable toxicity to carboplatin, then carboplatin treatment will be withheld or dose reduced.

Subjects with unacceptable toxic effects of one of the study drugs will receive only the tolerated drugs until disease progression.

- If patritumab/placebo needs to be discontinued, the subject will be withdrawn from the study
- In subjects whose cisplatin or carboplatin therapy is discontinued, reduced, or delayed, the patritumab and cetuximab will be continued and subjects will continue to undergo tumor assessments at 6 week intervals until disease progression or unacceptable toxicity
- In subjects whose cetuximab dose is discontinued, reduced, or delayed, the patritumab will be continued. Cisplatin or carboplatin will be administered for a maximum of 6 cycles
- In subjects whose cetuximab and cisplatin or carboplatin are either discontinued or delayed, patritumab will be continued as monotherapy

In addition to the recommendations provided below, please refer to the respective current prescribing information for detailed recommendations on managing suspected toxicities, for guidance on withholding, dose reductions, and discontinuation. If toxicities occur, it is up to the discretion of the Investigator to dose reduce or withhold one or more medications until recovery or resolution of the AE to Grade 0 or 1.

In individual cases, if a subject discontinues study drugs for an extended time period, the subject may restart study drugs at the discretion of the investigator after discussion with the Sponsor and CRO's medical monitors.

Investigators may contact the Sponsor's medical monitor to discuss any question regarding dose modification or discontinuation of study drugs.

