#### 6.2.8. Every 6 Weeks

- Frequency of tumor assessments will be every 6 weeks to Week 24 ( $\pm 3$  days); every 12 Weeks ( $\pm 7$  days) thereafter

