### **6.2.11. Discontinuation From Study Treatment**

Subjects discontinued from study treatment without documented (by imaging) PD, withdrawal of consent, death or loss to follow-up should continue tumor evaluation at 6-week intervals up to the first 24 weeks after randomization, then every 12 weeks ( $\pm 7$  days) until disease progression, start of new anticancer therapy, death, withdrawal of consent, loss to follow-up, or study closure.

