## 7. EFFICACY ASSESSMENTS

Tumor response assessments, including subjects who discontinued from treatment, will be performed every 6 weeks ( $\pm$  3 days) for the first 24 weeks independent of treatment cycle until disease progression, death, start of new anticancer therapy, withdrawal of subject consent, lost to follow-up, or study closure, whichever occurs first. After 24 weeks, tumor assessments will be performed every 12 weeks ( $\pm$  7 days).

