#### **17.3.2.8. Frequency of Tumor Re-evaluation**

In this study, tumor measurement will be conducted at Screening, and then at every 6 weeks for the first 24 weeks. After 24 weeks, tumor assessments will be performed every 12 weeks, or sooner if clinically indicated. Tumor measurement will be performed during the end of treatment visit unless it was performed within the previous 6 weeks or the previous assessment demonstrated disease progression.

Baseline tumor assessments must be performed within 2 weeks (14 days) prior to the first dose of treatment (Section 6.1.2). Existing radiographic scans can be used for the baseline evaluation if the scans were performed within 4 weeks prior to randomization.

All efforts should be made to ensure consistency between the baseline measurements and all subsequent measurements in reference to utilization of scanning method, equipment, technique (including slice thickness and field of view), and radiographic interpreter.

The radiographic evaluation must include CT or MRI scanning of the chest and abdomen. Any additional suspected sites of disease should also be imaged. All evaluations should meet the standard of care for imaging of lesions in the respective organ(s) and should conform to the image acquisition guidelines according to institutional standards.

All target and non-target sites are evaluated at each time point of tumor assessment.

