p Cisplatin infusions administered at 100 mg/m^2 IV over 1 hour and every 3 weeks up to a maximum of 6 cycles. For pre- and post-treatment hydration see [Section 3.1.2.1](#) and according to institutional standards. Creatinine clearance required prior to cisplatin administration. Cisplatin administered 1 hour after cetuximab administration. If carboplatin is selected instead of cisplatin, administer carboplatin at AUC of 5 over 30-60 minutes every 3 weeks for a maximum of 6 cycles. See [Section 3.1.2.1](#) for carboplatin.

q Genetic sampling is optional.

- r Tumor measurements will be assessed per RECIST Version 1.1. Baseline scans to be performed as part of eligibility during Screening. Existing radiographic scans can be used for the baseline evaluation if the scans were performed within 4 weeks prior to randomization.
  - s Tumor assessments are to be performed every 6 weeks to Week 24 (+/- 3 days), then every 12 weeks (+/- 7 days) thereafter.
  - t After discontinuation from study treatment, follow-up information for survival will be obtained per telephone approximately every 3 months for a minimum of 13 months.
  - u Additional biomarker samples:
    - Collect blood sample for cfDNA predose Cycle 1 Day 1, predose Cycle 2 Day 1, End of Cycle 6, predose every 4 Cycles, at progression (end of study treatment), and 40 days after last dose of study drug administered.
    - Collect blood samples for exosome at: predose Cycle 1 Day 1, predose Cycle 2 Day 1, and End of Cycle 6. Refer to the laboratory manual for instructions on collection and management of samples.
- \* Can be collected on Days 8 and 15 in all subsequent cycles at the discretion of the Investigator.
- † Corresponds to Cycle 1, Day 21 (504 hrs)—see [Table 8.2](#).

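### Section 5.1.7 gives subjects whose platinum is changed a scan interval after Week 24 that contradicts the single calendar set everywhere else for the primary endpoint

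*Protocol*

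**What the plan says.** The conflicting rule is a bullet in protocol Section 5.1.7. Its trigger is any platinum change: "In subjects whose cisplatin or carboplatin therapy is discontinued, reduced, or delayed, the patritumab and cetuximab will be continued". For these subjects it then says that "subjects will continue to undergo tumor assessments at 6 week intervals until disease progression or unacceptable toxicity". It does not mention Week 24.

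The rest of the plan describes one calendar for everyone:

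- Section 7: "Tumor response assessments, including subjects who discontinued from treatment, will be performed every 6 weeks" for the first 24 weeks, independent of treatment cycle. Then: "After 24 weeks, tumor assessments will be performed every 12 weeks".
- Section 6.2.8: "Frequency of tumor assessments will be every 6 weeks to Week 24", and 12-weekly thereafter.
- Section 6.2.11: subjects who stop treatment without imaging-documented progression "should continue tumor evaluation at 6-week intervals up to the first 24 weeks after randomization, then every 12 weeks".
- Section 17.3.2.8: "After 24 weeks, tumor assessments will be performed every 12 weeks, or sooner if clinically indicated".
- Table 17.2, footnote s: "Tumor assessments are to be performed every 6 weeks to Week 24 (+/- 3 days), then every 12 weeks (+/- 7 days) thereafter".
- SAP Section 5.1 repeats the Section 7 calendar.

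Sections 6.2.11 and 7 end scanning at progression, death, new anticancer therapy, withdrawal of consent, loss to follow-up or study closure. Toxicity is not on either list.

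**The concern.** PFS is dated at the scan that first documents progression (Section 7.1). A subject scanned 6-weekly after Week 24 will, on average, have the same true progression recorded earlier than one scanned 12-weekly. If the interval is set by whether platinum was changed, and platinum changes are more common in one arm, the arms are measured on different clocks for a reason unrelated to tumor growth. That is evaluation-time bias in the primary endpoint.

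The trigger need not be rare. Table 5.5 calls for a cisplatin delay at Grade 1 thrombocytopenia or Grade 2 neutropenia. Platinum is limited to 6 cycles of 21 days, nominally 18 weeks, so most triggers would occur before Week 24 and the two calendars would separate afterwards.

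The same sentence holds a second ambiguity. If its toxicity end point applies to scanning, it conflicts with Sections 6.2.11 and 7, which continue scans after treatment stops.

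An investigator managing a platinum change would consult Section 5.1.7. Section 6.4 allows no deviation from protocol procedures except for an immediate hazard, so after Week 24 either choice breaches a written instruction.

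**Working it through.** **Design figures (context; not disputed).** From protocol Section 11.10: medians 4.2 and 7.5 months, HR 4.2/7.5 = 0.56, one-sided alpha 0.10, 80% power, 1:1 allocation, 70 HRG-high subjects. Schoenfeld events = 4(1.2816 + 0.8416)² / (ln 0.56)² = 53.6, against the stated 53. Power is 79.6% with 53 events. It is 80.7% with 75 events at one-sided 0.05, against the stated 81%. The plan's figures reproduce.

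**Where the rules differ.** They agree up to Week 24, which is 24 × 7/30.4 = 5.53 months. Assuming exponential PFS at the design medians, the event-free proportion at that point is:

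- control: exp(−ln 2 × 5.53/4.2) = 0.40, about 14 of 35 HRG-high subjects;
- patritumab: exp(−ln 2 × 5.53/7.5) = 0.60, about 21 of 35.

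These are all subjects still event-free. Those exposed to the conflict are the subset who also had a platinum change, at a site that follows 5.1.7 literally. The documents give no figure for that subset.

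**Detection delay.** With scan interval I weeks and weekly hazard λ = (ln 2/median) × 7/30.4, the mean delay from true to documented progression is I/(1 − exp(−λI)) − 1/λ.

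| Median (months) | 6-weekly | 12-weekly | Difference |
|---|---|---|---|
| 4.2 | 3.11 weeks | 6.45 weeks | 3.34 weeks |
| 7.5 | 3.06 weeks | 6.26 weeks | 3.19 weeks |

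So an affected progression date moves by a little over 3 weeks on average.

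**Effect on the test.** This was simulated with 35 subjects per arm, 12-month accrual, a 22-month cut-off, progression seen only at scans, and an unstratified log-rank test at one-sided 0.10. There was no dropout and no separate deaths. Each setting had 4,000 runs, so the Monte Carlo standard error near 0.10 is √(0.1 × 0.9/4000) = 0.005. Shares are the proportion scanned 6-weekly after Week 24. Type I error uses a 4.2-month median in both arms; power uses 7.5 against 4.2.

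| Share, patritumab / control | Type I error | Power |
|---|---|---|
| 0% / 0% | 0.106 | 0.82 |
| 50% / 50% | 0.100 | 0.82 |
| 100% / 100% | 0.097 | 0.82 |
| 70% / 30% | 0.090 | 0.79 |
| 30% / 70% | 0.123 | 0.84 |
| 100% / 0% | 0.069 | 0.76 |
| 0% / 100% | 0.163 | 0.87 |

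**Effect on the hazard ratio with no true effect.** This is a large-sample Mantel-Haenszel-type HR (patritumab to control) on the 6-week grid to Week 96, at a common median of 4.2 or 7.5 months:

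- 60% / 40%: about 1.01
- 70% / 30%: 1.02-1.03
- 30% / 70%: 0.97-0.98
- 100% / 0%: 1.05-1.07
- 0% / 100%: 0.94-0.95

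**The case against.** The strongest reply is that 5.1.7 is loose wording rather than a second schedule. The bullet speaks of continuing assessments, which can mean carrying on as planned. The protocol itself uses an every-6-weeks label for the 6-then-12-weekly calendar, both in the heading of Section 6.2.8 and as a column title in Table 17.2. Section 7 is the efficacy section, expressly covers subjects off treatment, and is matched by the SAP. That reading is plausible, but the bullet does not say it and no order of precedence is given.

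The bias argument also has real limits. The trial is double-blind, both arms share the platinum backbone, and no difference in platinum changes between arms is documented. With 53 events the standard error of log HR is about 2/√53 = 0.27, so a 2-3% shift is roughly a tenth of a standard error. If adding patritumab caused more platinum changes, its progressions would be dated earlier and the bias would run against patritumab; inflated type I error needs more changes in the control arm. These points stand and keep the size modest.

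A reader might infer that the plan makes scan frequency depend on toxicity by design. It does not: every other passage sets a common calendar, and dependence arises only where a site puts 5.1.7 first. A reader might also infer that completing six cycles counts as discontinuation and so brings in nearly everyone. The text does not say so, the bullet follows a sentence about unacceptable toxic effects, and on that reading both arms would largely share one schedule, so the imbalance would mostly disappear.

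**Conclusion.** The contradiction is certain on the text: for subjects whose platinum is changed, the protocol gives two incompatible scan intervals after Week 24 for the primary endpoint. Whether it biases the result is not established. That requires sites to follow 5.1.7 literally and the rate of platinum changes to differ between arms; the documents inform neither.

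Under the stated assumptions, equal shares leave the one-sided error near its nominal 0.10. A 70/30 split moves it to about 0.09 or 0.12, with an HR shift of about 2-3%. The all-versus-none bound is about 0.07 to 0.16, with an HR shift of about 5-7%, in either direction. Power lies between 0.76 and 0.87 across the settings, and the 53-event target is unaffected.

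It would be too strong to conclude that scans stop at toxicity and later progressions are lost. The toxicity wording may instead limit how long patritumab and cetuximab continue, and Sections 6.2.11 and 7 require scans after treatment stops. The point should be corrected because it concerns the primary endpoint and the remedy is cheap, not because a large bias has been shown.

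**What to change.** Reconcile Section 5.1.7 with Section 7 by replacing only its tumor-assessment clause with, for example: *tumor assessments will continue on the Section 7 schedule, counted from randomization, until one of the stopping reasons listed in Section 7, regardless of which study drugs are reduced, delayed or stopped.* Referring to Section 7's full list matters: naming progression alone would omit death, new anticancer therapy, withdrawal of consent, loss to follow-up and study closure, and so create a new inconsistency.

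The sponsor should state separately whether the toxicity wording in that bullet refers to continuing treatment or to scanning. No change to the treatment rule is proposed here.

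The cost is one amended sentence and a clarification, with the usual amendment review. Affected subjects would have fewer scans after Week 24 than 5.1.7 read literally requires. Sample size and planned analyses do not change.

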### 5.1.7.1. Dose Modification of Patritumab

Patritumab is contraindicated for subjects with known hypersensitivity to either the drug substance or inactive ingredients in the drug product. In previous patritumab studies, the most common toxicities that occurred were rash, diarrhea, vomiting, nausea, fatigue, dyspnea, and skin and subcutaneous tissue disorders. Table 5.1 and Table 5.2 pertain to patritumab dose modifications.

If the initial loading dose of 18 mg/kg is not tolerated, infusion time can be extended to a maximum of 120 minutes for subjects unable to tolerate the 60 minute infusion. Patritumab/placebo is to be withheld from a subject experiencing a CTCAE Grade 3 AE, and resumed at the next regularly scheduled patritumab dosing (maintenance dose of 9 mg/kg) only after resolution of the AE to Grade 0 or 1 (or baseline grade if higher than Grade 1).

If a rash or mucositis occurs following the initial dose of patritumab 18 mg/kg, then hold the patritumab until the AE resolves to Grade 0 or 1 (or baseline grade if higher than Grade 1). If the rash or mucositis has not resolved, then hold cetuximab 250 mg/m^2 until the AE resolves to Grade 0 or 1 (or baseline grade if higher than Grade 1). If a rash or mucositis occurs on the maintenance dose of patritumab at 9 mg/kg, hold patritumab until the AE resolves to Grade 0 or 1 (or baseline grade if higher than Grade 1) and then decrease patritumab dosing to 6 mg/kg. If the AE does not resolve, hold the next dose of cetuximab until resolution to Grade 0 or 1 (or baseline grade if higher than Grade 1).

Left ventricular ejection fraction will be monitored throughout the study (see Section 9.11.1) for possible effects of patritumab treatment on cardiac function. Dose modification or suspension of patritumab treatment will be based on decreased LVEF, as outlined in Table 5.1.

For cases of ILD, refer to Section 9.3.2.

Both patritumab/placebo are to be withheld from a subject experiencing a Grade 4 AE.

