**Table 5.1: Patritumab Maintenance Dose Modification for Toxicities**

Toxicity	Withhold Criteria	Resumption Criteria	Dose Reduction Criteria	Discontinuation Criteria
All AEs a	Grade 3 or higher	Grade 0 or 1 (or baseline grade if higher than Grade 1) b	Reduce patritumab maintenance dose from 9 mg/kg to 6 mg/kg (for mucositis follow dose modification as defined above)	Failure to recover within 3 weeks

Toxicity	Withhold Criteria	Resumption Criteria	Dose Reduction Criteria	Discontinuation Criteria
Ejection fraction	Grade greater than or equal to 3, (LVEF of less than 40% or LVEF decrease of more than 20% from the baseline)	LVEF of at least 50% (or baseline) based on a repeat echocardiogram or MUGA scan performed in 3 weeks	Reduce patritumab maintenance dose from 9 mg/kg to 6 mg/kg	LVEF that does not recover within 3 weeks: Decreased $\geq$ Grade 3 <40% >20% decrease from baseline

a For elevations of aminotransferase (AST/ALT) and/or bilirubin, please see Section 4.1.4.

b Patritumab/placebo dosing may be resumed upon consultation with the Sponsor's medical monitor if the event has resolved to Grade 2.

MUGA = multigated acquisition (scan); LVEF = left ventricular ejection fraction.

Dose delays/reductions for toxicities related to patritumab are summarized in Table 5.2.

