**Table 5.2: Dose Delays/Reductions for Toxicities Related to Patritumab**

Grade	Action
1	Continue current dose level
2	Continue current dose level
3	Discontinue patritumab/placebo for up to 3 weeks until the event has recovered to Grade 1 or baseline. a Administer patritumab at a dose that is decreased by one dose level for subsequent cycles. A maximum of 1 dose reduction from the 9 mg/kg IV maintenance dose to 6 mg/kg IV maintenance dose will be permitted. No dose reductions below patritumab 6 mg/kg will be allowed.
4	Discontinue patritumab/placebo for up to 3 weeks until the event recovers to Grade 1 or baseline. a Discuss the event with the sponsor's Medical Monitor or designee before restarting patritumab/placebo. If the investigator and the sponsor's Medical Monitor/designee agree, the weekly maintenance dose will also be decreased from 9 mg/kg IV to 6 mg/kg IV.

a If the subject fails to recover to Grade 1 or baseline and dose must be delayed >3 weeks, the subject will be withdrawn from all study treatment, but should continue to undergo all follow-up evaluations

To receive patritumab, a subject's ANC must be  $\geq 1.5 \times 10^9/L$  ( $\geq 1500/mm^3$ ) and platelet count must be  $\geq 100 \times 10^9/L$  ( $\geq 100,000/mm^3$ ). Patritumab may be withheld for up to 3 weeks to allow cell counts to recover to these values. Dose administration may be delayed no more than 3 weeks to allow for recovery. If the dose is delayed more than 3 weeks, the subject will be withdrawn from study treatment, unless discussed and agreed with the sponsor.

All subjects should be carefully monitored for possible infusion reactions during the administration of patritumab/placebo. If, during infusion, a subject experiences mild to moderate symptoms suggestive of infusion reaction (such as fever and chills, with or without nausea/vomiting, pain, headache, dizziness, dyspnea, hypotension), slow down the infusion up to 120 minutes (see Section 3.1.2.1 for administration of patritumab/placebo). All subsequent infusions should be administered at the same slow rate (up to 120 minutes).

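### The rash and mucositis rule in Protocol 5.1.7.1 gives no onset grade and contradicts Table 5.2 at low grades and, for rash, the Grade 3 withhold threshold of Table 5.1

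*Protocol*

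**What the plan says.** Four provisions of the Protocol bear on rash and mucositis under patritumab.

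- **Section 5.1.7.1, rash and mucositis paragraph.** On the maintenance dose: "If a rash or mucositis occurs on the maintenance dose of patritumab at 9 mg/kg, hold patritumab" until the event is back to Grade 0 or 1 (or to baseline if that was higher), "and then decrease patritumab dosing to 6 mg/kg". After the loading dose: "If a rash or mucositis occurs following the initial dose of patritumab 18 mg/kg, then hold the patritumab", with the same recovery criterion and no reduction stated. Neither sentence gives an onset grade or asks whether the event is attributed to patritumab.
- **Section 5.1.7.1, general rule.** "Patritumab/placebo is to be withheld from a subject experiencing a CTCAE Grade 3 AE". Grade 4 has its own sentence.
- **Table 5.1**, row for all adverse events. The withhold criterion is "Grade 3 or higher". The dose reduction cell lowers the maintenance dose from 9 to 6 mg/kg and adds "for mucositis follow dose modification as defined above". Rash has no such cross-reference.
- **Table 5.2**, titled "Dose Delays/Reductions for Toxicities Related to Patritumab". The action at Grade 1 and at Grade 2 is "Continue current dose level". No toxicity is excepted.

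Section 5.1.7.1 introduces both tables as applying to patritumab dose modification and gives no order of precedence between them and the text.

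**The concern.** These are operative dosing instructions for the experimental drug, and at low grades they point in different directions. The same section names rash first among the common toxicities seen with patritumab, so the situation is likely to arise.

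What is at stake is consistency of exposure within the patritumab arm. Two sites could treat the same Grade 2 rash differently, and each could cite the Protocol. Section 6.4 does not allow deviations except to remove an immediate hazard, and the per-protocol set (Protocol 11.1.2, SAP 6.1.3) depends on sufficient compliance, whose criteria are still to be finalized. At Grade 2, following one provision means departing from the other. The relative dose intensity summary in SAP 8.3.6 would then mix real toxicity with differences in how sites read the rule.

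**Working it through.** No sample size, power or alpha figure in the plan rests on this point. The check is a comparison of the provisions, followed by the size of the dose step.

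**Step 1. The provisions side by side, for an event on the 9 mg/kg maintenance dose.**

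| Event | Text of 5.1.7.1 | Table 5.1 | Table 5.2 (if patritumab-related) |
|---|---|---|---|
| Grade 1 rash | Recovery criterion already met, so the hold has no effect; read literally, reduce to 6 mg/kg | Below the withhold threshold | Continue |
| Grade 2 rash | Hold, then 6 mg/kg | Below the withhold threshold | Continue |
| Grade 1 mucositis | As for Grade 1 rash | Reduction referred back to the text; hold threshold unclear | Continue |
| Grade 2 mucositis | Hold, then 6 mg/kg | Reduction referred back to the text; hold threshold unclear | Continue |
| Grade 3 rash or mucositis | Hold, then 6 mg/kg | Hold, then 6 mg/kg | Hold, then 6 mg/kg |

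The provisions agree at Grade 3.

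- **Hold.** The conflict with Table 5.2 has practical effect at Grade 2, for rash and mucositis alike.
- **Reduction.** The conflict with Table 5.2 is at Grade 2 and, on a literal reading, also at Grade 1.
- **Table 5.1.** The conflict is clear for rash only. For mucositis the table defers to the text on reduction. Because that note sits in the reduction column, it is unclear whether the Grade 3 withhold threshold is replaced as well.
- **Attribution.** Table 5.2 covers patritumab-related toxicities; the text paragraph has no such condition. For an event not attributed to patritumab, Table 5.2 is silent and only the comparison with Table 5.1 remains.
- **After the loading dose.** The text says hold only, again with no onset grade. The hold-then-reduce sequence belongs to the maintenance dose.

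**Step 2. Size of the dose step.** Inputs: 9 mg/kg and 6 mg/kg (Section 5.1.7.1).

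1 − 6/9 = 0.333, that is 33% less per later maintenance dose.

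**Step 3. Illustration of cumulative dose for one affected patritumab subject.** Assumptions, not from the documents: n = 6 to 10 cycles in total, event after the dose of cycle k = 2, 3 or 4, and every later dose at 6 mg/kg.

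- Unreduced total: 18 + 9(n − 1)
- Reduced, no dose missed: 18 + 9(k − 1) + 6(n − k)
- Reduced, one dose missed: 18 + 9(k − 1) + 6(n − k − 1)

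| n | k | Unreduced (mg/kg) | No dose missed | One dose missed |
|---|---|---|---|---|
| 6 | 2 | 63 | 51 (81.0%) | 45 (71.4%) |
| 6 | 4 | 63 | 57 (90.5%) | 51 (81.0%) |
| 10 | 2 | 99 | 75 (75.8%) | 69 (69.7%) |
| 10 | 4 | 99 | 81 (81.8%) | 75 (75.8%) |

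Across the assumed range, such a subject receives about 76% to 90% of the unreduced total with no dose missed, and about 70% to 81% with one dose missed.

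**Step 4. Arm level.** This would need the rate of Grade 1–2 rash and mucositis on maintenance dosing and the share of sites following each rule. The documents give neither, so no arm-level figure can be computed.

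**The case against.** The strongest defence is that Section 5.1.7 is headed as guidelines. It asks the investigator first to attribute each toxicity to a drug, allows discretion to reduce or withhold, and offers the medical monitor for questions. Severe acneiform rash under cetuximab has its own table (Table 5.4). All of this softens the practical effect. None of it says which written rule governs a patritumab-related Grade 2 rash, so the contradiction stands.

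The paragraph might also be read as tacitly meaning Grade 3, since it follows the general Grade 3 rule. That is hard to sustain. The Grade 3 hold is already stated, the rash and mucositis rule is written separately, and Table 5.1 treats it as a distinct rule for mucositis.

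The consequences are limited. Protocol 1.1.1.4 considers exposure after a step down to 6 mg/kg likely to remain in the range of the threshold concentration. The primary analysis is as randomized in the HRG-high stratum of the FAS, and SAP 8.3.6 summarizes dose reductions and relative dose intensity, so differences would be visible, though not their cause. These points stand.

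A reader might infer three stronger things that the documents do not support:

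- **That Table 5.1 also tells sites to continue at Grades 1–2.** It has no such instruction. Continuation follows only by implication from its threshold; the explicit instruction is in Table 5.2.
- **That the conflict makes the arms differ in experimental-drug exposure.** Control subjects receive placebo, and the rule is applied blind. The exposure issue is variation within the patritumab arm.
- **That a large share of all subjects would be underdosed.** No rate is given. An effect also requires assignment to patritumab (about half of subjects under 1:1 allocation), an event on maintenance dosing, and a site that follows the text.

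**Conclusion.** The contradiction is real. For a patritumab-related Grade 2 rash or mucositis on the maintenance dose, Section 5.1.7.1 and Table 5.2 cannot both be followed; read literally, the reduction clause extends this to Grade 1. For rash there is a second conflict, with the Grade 3 withhold threshold of Table 5.1. For mucositis, Table 5.1 defers to the text on reduction and is unclear on the hold.

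The size is 33% less drug per later maintenance dose for an affected subject on patritumab, depending on the provision the site follows. The cumulative figures are illustrations under assumed cycle numbers. No effect on the arm, on power or on the primary result can be derived. This is an internal inconsistency that should be cleared up; it does not threaten the validity of the primary test.

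**What to change.** Reconcile the rash and mucositis paragraph of Section 5.1.7.1 with Tables 5.1 and 5.2 so that one rule governs. The revised text should state:

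- the onset grade at which a hold applies and the onset grade at which a reduction applies, separately for the loading and maintenance doses;
- whether the rule depends on attribution to patritumab;
- whether rash and mucositis follow the same rule, and whether the mucositis note in Table 5.1 also changes the withhold threshold;
- which provision takes precedence if the text and a table differ.

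The sponsor's clinical team decides the rule; no view is given here on which one is right. The cost is a protocol clarification and a notice to sites, with no change to sample size or to the planned analyses.
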